6.2.2. Diagnoses

The system that is used to classify and code all the diagnoses for indication, is the International Classification of Diseases (ICD-10).

Definition of indications: could be classified into three groups of indications; authorized, unauthorized with scientific evidence, unauthorized without scientific evidence and indications with unknown evidence.

An analysis of the indications for immunoglobulins will be carried out, for which the indications will be classified into three groups based on a bibliographic review of the current guidelines of UK and of CatSalut, see annexes 4 and 5.

- authorized indications (group 1): authorized by the EMA
- unauthorized indications with scientific evidence (group 2): not authorized by the EMA and used off-label with scientific evidentiary support (level A) (Oxford Centre for Evidence-based Medicine): at least one controlled and randomized clinical trial (UK Ia, Ib)
- unauthorized indications without scientific evidence (group 3): not authorized by the EMA and unaccepted indications
- indications with unknown evidence (group 4)

The trade names of immunoglobulines relating to approved indications are shown in annex 6.

The proportion of patients for each indication will be calculated as well as the proportion of patients in each group.

6.2.3. Costs

To estimate the costs of a certain indication per patient the yearly mean costs per gram of immunoglobulins are used.

The following calculation is used:

Weight of a patient (kg) x dosage (0,4-0,8g/kg) x price (€/g) = price per months per patient (€)

Price per administration (€) x 13 administration = price per year per patient (€)

Total cost (€) per person-month over the whole study period

With this, the costs per patient per month and per year could be calculated. At the end, the costs of different indications could be estimated through the mean costs per indication per patient and per person-month.

For the Vall d'Hebron Hospital the costs are as following:

Year	€/g overall	€/g intravascular	€/g extravascular
------	-------------	-------------------	-------------------

2019	42,75	42,77	42,33
2020	42.33	42,33	42,32
2021	41.60	41,53	42,36

These costs are obtained through the sum of the total costs per brand divided by the total stock per brand multiplied by the grams per brand.

The costs per year (€/g) could be different between hospitals due to institutional agreements with the pharmaceutical industry providers.

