6.1.1. Base population

The inclusion criteria are: all the naive incident users who initiate a treatment with non-specific immunoglobulins (J06BA01 and J06BA02) in the period between September 2019 and December 2021 regardless of their age, sex, indication, dose and duration. And without immunoglobulins use in the year before the treatment initiation date.

A preliminary count of registered treatments indicates that around 500 patients would meet these inclusion criteria.

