6.2.4. Statistical analysis

Standard descriptive calculations for qualitative and quantitative variables will be used. The median of general characteristics such as age, follow-up period and treatment duration will be calculated. The gender distribution is also mapped out. Furthermore, calculations are also made with the patients who switch, *see paragraph 6.2.1*. Here, the number of switches, the mean time between switching and the number of switches per patient are mapped out. This will be visualized with a Kaplan Meier curve.

The proportion of patients for each indication will be calculated as well as the proportion of patients in each group. Information will also be calculated by person-month.

The analysis will be stratified following the variable list in the next section.

The result tables of this objective are shown in annex 7.

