8.2. Strengths and limitations because of datasource

The strength of the RPT is that the register is implemented in Catalonia by health professionals from the Comprehensive Public Health System of Catalonia (SIS CAT) to carry out the task of monitoring the data on the use of high-cost drugs in normal clinical practice conditions. It consists of three levels of information: treatment level, initiation level and follow-up level. Just the availability of the RPT represents opportunities for analysis and the generation of support information for management decision-making.

There are also some limitations regarding the data source. The database that is used is specific for Catalonia and only Catsalut hospitals participate, which means that the generalizability is limited. In addition, it has only been mandatory since 2019 to register immunoglobulins in the RPT, for that reason the data source is relatively new and possibly less reliable. This also means that no information was available before 2019 about the use of immunoglobulins in the RPT, which again could lead to decreased reliability of the results. A possible other limitation is that different clinicians provide the RPT with information, the consistency of the database could therefore be questioned. Moreover, there is limited information available about the costs as they may vary across different brands (which are not present in the RPT registry), thus the yearly mean costs are used. Thereby, it is assumed that the administrations are given monthly based on the data extraction (dose/month). The reliability of this information could be questioned: some immunoglobulins require weekly/biweekly administrations.

9. Results spreading plan

The knowledge and results obtained because of this study will be disseminated through conferences, internal talks, journals and as training material.

References

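### The monthly and yearly cost lines in SAP section 6.2.3 use conflicting time units (8.3% apart), and the dose source and the person-month numerator are not defined

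*SAP*

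**What the plan says.** Section 6.2.3 sets out the costing in three lines. The first is "Weight of a patient (kg) x dosage (0,4-0,8g/kg) x price (€/g) = price per months per patient". The second is "Price per administration (€) x 13 administration = price per year per patient". The third is "Total cost (€) per person-month over the whole study period", with no statement of how the total is formed. The section then says that "the costs of different indications could be estimated through the mean costs per indication per patient and per person-month". It tabulates €/g by year and route for HUVH only and notes that prices may differ between hospitals.

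Section 8.2, on limitations of the data source, says that "it is assumed that the administrations are given monthly based on the data extraction (dose/month") and concedes that "some immunoglobulins require weekly/biweekly administrations". It does not mention 13.

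Two other places bear on duration. Section 6.1.1 admits patients "regardless of their age, sex, indication, dose and duration". Section 6.2.4 says: "The median of general characteristics such as age, follow-up period and treatment duration will be calculated". Treatment time is therefore expected to be available for each patient.

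**The concern.** The first line produces a price per month. The second starts from a price per administration. No other line produces a price per administration, so both labels refer to the same product. That product can be monthly or four-weekly, but not both, and the annual multiplier depends on which it is.

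Three further gaps lie in the same lines:

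- The dose enters as a range, with no rule for the value that applies to a given patient. Section 8.2 points to a different source, the extracted dose per month.
- The yearly line contains no treatment time, although duration is unrestricted in the cohort.
- The person-month cost has a denominator but no defined numerator.

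The high cost of immunoglobulins is a stated motive of the study (sections 4.1 and 4.2), and cost per indication is a planned output under the methods for objective 1. As written, two analysts could follow the SAP and report different monthly, yearly and person-month costs from the same data.

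**Working it through.** **Inputs.** The dose range of 0.4 to 0.8 g/kg, the multiplier of 13 and the 2021 overall HUVH price of 41.60 €/g come from section 6.2.3. Monthly administration comes from section 8.2. The enrolment window of September 2019 to December 2021 (4 + 12 + 12 = 28 months) comes from section 6.1.1. A body weight of 70 kg is an assumption, because the SAP gives no weight. It affects the euro amounts but none of the ratios.

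**1. The plan's own figure.** The SAP gives no worked cost total, so the multiplier of 13 is the only figure that can be checked.

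- Monthly administration, as stated: 12 a year. This does not reproduce 13.
- One administration every 28 days: 365.25 / 28 = 13.04. This reproduces 13, but the SAP states no such interval.

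**2. Size of the mismatch.** 13 / 12 = 1.083, or 8.3%, whatever the weight, dose or price.

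| | 0.4 g/kg | 0.8 g/kg |
|---|---|---|
| First line: 70 × dose × 41.60 | €1,164.80 | €2,329.60 |
| × 12 | €13,977.60 | €27,955.20 |
| × 13 | €15,142.40 | €30,284.80 |
| Difference per patient-year | €1,164.80 | €2,329.60 |

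If the first line is really four-weekly, the yearly amount is the × 13 row. The calendar-month cost is then 13/12 of the first line: €1,164.80 × 13/12 = €1,261.87 at 0.4 g/kg. The amount labelled monthly would be too low by that factor.

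**3. Dose range.** 0.8 / 0.4 = 2.0. The unresolved range moves every cost by up to a factor of 2. By comparison, the HUVH prices tabulated by route and year run from 41.53 to 42.77 €/g, a spread of 3%.

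**4. Duration.** Suppose the × 13 amount were recorded as the cost a patient incurred. Its ratio to the first-line amount times months treated would be 13 / months. The durations below are illustrative.

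| Months treated | 1 | 3 | 6 | 12 | 28 |
|---|---|---|---|---|---|
| Ratio | 13.0 | 4.33 | 2.17 | 1.08 | 0.46 |

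**5. Person-month numerator.** Take one patient treated for 6 months at 0.4 g/kg.

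- If the total is the first line × months, the result is 1,164.80 × 6 / 6 = €1,164.80 per month.
- If the total is the yearly line, the result is 15,142.40 / 6 = €2,523.73 per month.

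The SAP does not say which applies.

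**The case against.** Several points on the other side carry weight.

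- **13 may simply mean every four weeks.** The number is not wrong in itself. But the first line is then not monthly, so one of the two labels is still wrong.
- **The limitation is disclosed.** Section 8.2 admits that cost information is limited, that monthly administration is assumed and that some products are given more often. That is fair disclosure, but it does not reconcile 12 with 13.
- **The costing is modest.** Objective 1 in section 5 speaks of describing use and does not name cost. The costing is descriptive, and no hypothesis or decision depends on it. A constant 12 or 13 also cancels when indications are compared, so the 8.3% affects the absolute level only.

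A reader might also infer more than the SAP supports:

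- **That the costing ignores recorded dose and duration.** Costs per person-month are also planned, so treatment time enters that denominator, and section 8.2 links the calculation to an extracted dose per month. What is shown is that the written formula does not use that dose and that the yearly line has no duration term.
- **That a patient treated for one month is charged 13 times the cost.** Nothing says the yearly amount is booked as incurred cost. It reads naturally as an annualised rate, so the ratios in step 4 are conditional.
- **That cost per indication reflects mainly body weight, or that indications would be ranked wrongly.** The first assumes one g/kg value for everyone, which the SAP does not state. No ranking is planned.
- **That patients without a recorded weight would have no cost.** Section 6.4.1 rules out imputation, but section 6.6 has missingness checked and queried with the centres. No figure suggests that weight is often absent.

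**Conclusion.** The concern stands in a limited form. Sections 6.2.3 and 8.2 conflict on the time unit, and the planned monthly and yearly costs disagree by 8.3% at any weight, dose or price. That result needs no assumption beyond the SAP's own text. The dose input is a twofold range with no selection rule, while another section points to an extracted dose per month. The numerator of the person-month cost is undefined. The yearly line is acceptable only as an annualised rate. Used as incurred cost, it would misstate courses shorter or longer than a year, from 13 times at one month to 0.46 times at 28 months.

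The euro amounts rest on an assumed 70 kg and one hospital's 2021 price. The annexes with the variable extraction table and the result shells are not shown, so the availability of dose per month for each patient rests on the wording of section 8.2 alone. This concerns costing only; no dose or administration interval is judged. It should be settled before any cost is computed.

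**What to change.** Reconcile sections 6.2.3 and 8.2, and rewrite the costing as follows:

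1. **One time unit.** Either the first line is a monthly cost and the year is 12 times it, or it is a four-weekly cost, the year is 13 times it and the calendar month is 13/12 of it. State which.
2. **Source of dose.** Where the extraction holds dose per month for each patient, compute cost as recorded grams per month × the €/g of that hospital, year and route, summed over treatment months. State the unit in which dose per month is held. Keep the weight-based calculation only as a labelled fallback, with a rule for the g/kg value it uses.
3. **Cost per person-month.** Define it as total cost / total treatment months, overall and by indication.
4. **Yearly figure.** Label it as annualised, and do not report it as the cost a patient incurred.

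The cost is a revision of section 6.2.3 and a change to the analysis script. Start and end dates are already needed for treatment duration. The new requirement is €/g by year and route from HUB and HGTiP, because the SAP tabulates HUVH only. If dose per month turns out not to be held per patient, items 1, 3 and 4 still apply, and the SAP should say that all costs rest on an assumed dose.

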6.2.4. Statistical analysis

Standard descriptive calculations for qualitative and quantitative variables will be used. The median of general characteristics such as age, follow-up period and treatment duration will be calculated. The gender distribution is also mapped out. Furthermore, calculations are also made with the patients who switch, *see paragraph 6.2.1*. Here, the number of switches, the mean time between switching and the number of switches per patient are mapped out. This will be visualized with a Kaplan Meier curve.

The proportion of patients for each indication will be calculated as well as the proportion of patients in each group. Information will also be calculated by person-month.

The analysis will be stratified following the variable list in the next section.

The result tables of this objective are shown in annex 7.

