6.2.1. Exposures

All the patients included in the study are exposed to non-specific immunoglobulines, this could be an extra- (J06BA02) or intravascular (J06BA01) administration.

List of definitions:

Naive incident user: a patient who isn't exposed to immunoglobulines (intra- or extravascular) a year prior to the start of the treatment with a non-specific immunoglobulin.

Immunoglobulin switching: the patients who changed immunoglobulin therapy from extravascular to an intravascular administration or vice versa during the study period providing that the period in between therapies is less than a year, regardless of the indication. In cases where two immunoglobulin types overlap in time, we won't consider them as switchers.

Immunoglobulin concomitance: if an overlapping use of an intravascular and an extravascular immunoglobulin of at least one day, regardless of indication. If cases are found they will be narratively described.

Immunoglobulin discontinuation: the patients who stopped the use of any type of non-specific immunoglobulines (J06BA01 and J06BA02) for a year or longer.

Duration of treatment: When there is a certain period between the start date and end date of the use of immunoglobulin.

Patients with multiple indications: In RPT each treatment initiation is linked to a single indication. When a patient meets multiple treatment initiations, different diagnosis for each may be found. In this case, if the patient does not meet any of the previous definitions (switching or discontinuation) and is treated with the same type of IGG administration (extra- or intravascular), they will be reviewed case by case. From this review, it will be decided based on medical criteria whether diagnoses are a specification of the other (e.g., transplant versus transplant rejection), or if they are clearly referring to different clinical entities. For both situations, if cases are found they will be narratively described.

These group of patients will not be taken into account during the validation of the RPT (see 6.3).

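### Treatment duration is summarised by a plain median with no censoring rule for patients still on treatment, which tends to bias it short; the one-year discontinuation rule and the switching curve also lack a stated data cut

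*SAP*

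**What the plan says.** - **Duration.** SAP section 6.2.1 defines it as follows: "When there is a certain period between the start date and end date of the use of immunoglobulin". Section 6.2.4 gives the summary: "The median of general characteristics such as age, follow-up period and treatment duration will be calculated". Neither section deals with a patient who has no end date because treatment continues. Section 6.4.1 rules out imputation.
- **Discontinuation.** Section 6.2.1 defines this group as "the patients who stopped the use of any type of non-specific immunoglobulines (J06BA01 and J06BA02) for a year or longer". It sets no minimum follow-up for confirming the gap.
- **Switching.** Section 6.2.1 counts a change of route "during the study period providing that the period in between therapies is less than a year, regardless of the indication". Section 6.2.4 turns to the patients who switch and says that "the number of switches, the mean time between switching and the number of switches per patient are mapped out". It adds: "This will be visualized with a Kaplan Meier curve".
- **Dates.** Section 6.1.1 includes users who start treatment "in the period between September 2019 and December 2021 regardless of their age, sex, indication, dose and duration". These dates govern initiation. No end of follow-up is given, and section 6.5 mentions only an undated last extraction.
- **Strata.** Section 6.2.4 applies the stratification variables to the analysis. Section 6.2.4.2 includes ICD-10 chapters among them.

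**The concern.** Time on treatment is right-censored for anyone still treated when the data stop. A plain median of start-to-end time has no place for such a patient. With no end date and no imputation, the programmer must either leave the patient out or substitute the data end date. The first choice keeps the shorter treatments, and the second counts unfinished treatments as finished.

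The error is not uniform. It is small where courses are short and large where treatment is long term. Describing use is objective 1, and results are split by ICD-10 chapter, so chronic indications would look closer to short-course ones than they are.

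Two related definitions have the same gap. A stop of a year or longer can be seen only if a year of data follows the last use. A mean time taken among switchers conditions on the switch having been observed, and the curve meant to accompany it is not defined well enough to be reproduced.

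**Working it through.** The SAP gives no figure for duration, discontinuation or switching, so there is none to reproduce. The figures below are illustrative.

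**Inputs**
- Initiation window: September 2019 to December 2021, which is 4 + 12 + 12 = 28 months (section 6.1.1).
- Cohort: about 500 patients (section 6.1.1).
- Discontinuation gap: 12 months (section 6.2.1).
- Assumed, because the SAP gives none of them: even entry over the 28 months; exponential duration with true median m; data cut at the end of December 2021, or 6 or 12 months later.

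**1. Truncated median.** Let E be the extra months of data after December 2021. The chance that a patient's available follow-up exceeds t is 1 for t ≤ E, and (28 + E − t)/28 after that. The truncated median solves 2^(−t/m) × P(follow-up > t) = 0.5.
- m = 12, E = 0, t = 7.0: 0.667 × 0.750 = 0.50.
- m = 24, E = 0, t = 9.6: 0.758 × 0.657 = 0.50.
- m = 24, E = 12, t = 17.1: 0.610 × 0.818 = 0.50.
- m = 12, E = 12: follow-up is never below 12 months, so the truncated median equals the true one.

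**2. Simulation of 1,000,000 patients** (medians in months):

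| True median | Data cut | Truncated | Completed only |
|---|---|---|---|
| 6 | Dec 2021 | 4.5 | 4.1 |
| 12 | Dec 2021 | 7.0 | 5.7 |
| 24 | Dec 2021 | 9.6 | 6.8 |
| 6 | +6 months | 6.0 | 4.8 |
| 12 | +6 months | 9.6 | 6.8 |
| 24 | +6 months | 13.4 | 8.3 |
| 6 | +12 months | 6.0 | 5.4 |
| 12 | +12 months | 12.0 | 8.2 |
| 24 | +12 months | 17.1 | 10.3 |

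On the same data with the December 2021 cut, the Kaplan-Meier median was 6.0, 12.0 and 24.1. The share still on treatment at that cut was 30%, 50% and 69%.

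**3. Effect on a comparison of strata.** Two strata with true medians of 24 and 6 months differ by a factor of 4. With the December 2021 cut, the truncated medians give 9.6/4.5 = 2.1 and the completed-only medians give 6.8/4.1 = 1.7.

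**4. Discontinuation.** A patient qualifies only if last use is at least 12 months before the cut. With a December 2021 cut, starters from January 2021 on cannot qualify. That is 12/28 = 43% of entry months, or about 500 × 12/28 = 214 patients under even entry. For true medians of 6, 12 and 24 months:
- December 2021 cut: 70%, 50% and 31% have stopped, but 31%, 20% and 11% meet the one-year rule.
- Twelve extra months: 93%, 75% and 52% have stopped, and 70%, 50% and 31% meet it.

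**5. Mean among observed events.** As a guide to any mean restricted to patients whose event was seen: with a true median of 12 months the true mean is 12/ln 2 = 17.3. The mean among those with the event by December 2021 is 7.1.

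**The case against.** Four points can be made for the plan.

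- **Switching.** A reader might infer that the plan ignores censoring here. It does not go that far: section 6.2.4 names a Kaplan-Meier curve, the standard tool for censored times. The wording about time between switches may also mean the interval between therapies rather than time from initiation to first switch, in which case the mean is not a biased estimate of the latter. This stands. What remains is that the curve has no risk set, origin or censoring date, and that the surrounding text is about switchers. A curve drawn in switchers alone would fall to zero by construction.
- **Late starters.** A reader might infer that nobody starting in 2021 can ever be classed as discontinued. The documents do not support this as a fact. The September 2019 to December 2021 dates define initiation, and data may extend beyond them. With 12 more months, late starters who stop early can qualify.
- **Too few discontinuations reported.** The visible text plans no discontinuation proportion. Section 6.2.1 uses the definition to sort patients with several indications, the registry holds separate discontinuation variables (section 6.1.2), and the result shells in Annex 7 are not shown. The point therefore applies only if such a proportion is tabulated.
- **Size.** The cohort covers every indication and duration. If most courses are short, or follow-up runs well past 2021, the truncated median is close to right. Median follow-up and person-month results also give some view of unequal observation. This limits the size of the bias, but it supplies no rule for ongoing patients, and completed-only medians are short in every row of the table.

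The end of follow-up may be fixed in the protocol, which is not shown, so its absence alone is not the fault. The fault is the choice of a plain median for a censored quantity.

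**Conclusion.** The point holds for treatment duration: the plan fixes an estimator that cannot represent patients still on treatment, and either way of forcing them into it tends to shorten the median, most for chronic indications. Under the stated assumptions and a December 2021 cut, a true 12 months would be reported as about 7.0 or 5.7, and a true 24 months as about 9.6 or 6.8. With 12 further months of data the truncated median is right up to a true 12 months, but still short, at about 17, for a true 24. The direction follows from the definitions; the size depends on a data cut and a duration distribution that the SAP does not give.

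For discontinuation, the definition cannot be confirmed for anyone whose last use lies within 12 months of the cut, wherever that cut falls. That this takes in every starter from January 2021 is conditional on data ending in December 2021. For switching, the fault is an unspecified curve beside a mean restricted to switchers. This should be corrected before analysis.

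**What to change.** 1. State the data cut in the SAP, for each hospital if the extraction dates differ.
2. In section 6.2.4, replace the plain median of treatment duration with a Kaplan-Meier median from initiation in all starters, censoring ongoing patients at the cut. Do the same within strata, and report the number still on treatment. Where the curve does not reach 50%, say that the median was not reached.
3. If one-year-gap discontinuation is reported, date the event at last use and censor at the cut minus 12 months, so that every counted event can be confirmed. Starters after that date then contribute no follow-up to this analysis, and their number should be given.
4. Define the switching curve as time from initiation to first switch in all starters, with non-switchers censored. Keep the mean among switchers only as a description labelled as such, and say which interval it measures.
5. Treating permanent stop or death as a competing event for switching is optional. It depends on whether those dates are captured, which the visible text does not show for death.

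The cost is a few sentences in sections 6.2.1 and 6.2.4 and standard survival code. The duration definition already requires start and end dates, so item 2 adds only the cut date. The variable extraction table (Annex 10) is not shown, so the sponsor should confirm that ongoing treatment can be told apart from a missing end date.
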